H5. There will also be a reduced bias towards sad emotional expressions (i.e. greater threshold change in favour of happy) following acute alcohol consumption compared to placebo (happy-sad 2AFC task).

Study Design

This is a placebo-controlled experimental study, which comprises one within-subjects factor of drink (0.4 g/kg alcohol, placebo) and one between-subjects factor of trait

anger (high, low). For the 6AFC task (see Measures and Materials), there will be an additional within-subjects factor of emotion (happy, sad, angry, disgust, surprise and fear). The primary dependent measures will be hit rate and false alarms (6AFC task) and threshold response (2AFC tasks). We will also take subjective measures of state aggression, mood and intoxication. For these outcomes, there will be an additional within-subjects factor of time (pre-consumption, post-consumption).

Study Site

School of Experimental Psychology, [name], Bristol University, [name].

Participants and Recruitment

Male and female social alcohol drinkers (n = 88; 50% male) will be recruited from the staff and students at the University of Bristol, and the general population. Participants will attend two sessions of approximately 75 minutes each. Participants will be recruited by existing email lists, poster and flyer advertisements, and by word of mouth. They will be asked to contact the researcher for further details of the study if they are interested in taking part. Those who meet the initial study inclusion criteria will be asked to complete a short online screening questionnaire. Participants that are eligible will be sent the information sheet, and asked to contact the researcher again if they would like to sign up for the study or if they require further information. Participants will be required to not drink alcohol 24 hours prior to the study session. On completion of the study, participants from the general population will be reimbursed £20 or equivalent course credits (if eligible).

Inclusion criteria

- Good physical and psychiatric health (self-report)
- Drinks between 5 and 35 alcoholic units* per week if female or between 10 and 50 alcoholic units* per week if male
- Aged between 18 and 40 years
- Be high or low in trait aggression, defined by a score above 41 and below 32 on the Anger Expression Index subscale of the State-Trait Anger Expression Inventory-2 (STAXI-2), respectively.
- Speaks English as first language or equivalent level of fluency

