- Able to attend two sessions, at least one week apart

* One unit equals one 25 ml single measure of spirit (ABV 40%), or a third of a pint of beer (ABV 5-6%) or half a standard (175 ml) glass of red wine (ABV 12%).

Exclusion criteria

- Alcohol consumption less than 24 hours prior to the study sessions
- Weight less than 50 kg if female or 60 kg if male
- Strong familial history of alcoholism defined as one or more immediate relative (parent, sibling) or more than one other relative (e.g., cousin, grandparent) (self-report)
- History of psychiatric disorder (including drug addiction) (self-report)

- Uncorrected visual impairment
- Uncorrected auditory impairment

Sample size determination

A sample size calculation based on previous findings from a study using a between-subjects design (Craig et al., 2009) indicates an effect size of $d = 1.0$ for the difference between alcohol and placebo on sadness recognition ($M = 0.14$, $SD = 0.02$; $M = 0.12$, $SD = 0.02$, respectively). These data indicate that we require a total sample size of 46 participants to achieve 90% power at an alpha level of 5%. As we are including a between-subjects factor, we plan to recruit sufficient numbers in each group to achieve this level of power to observe a main effect of alcohol. However, as this is likely to be an inflated effect size, we used a more conservative effect size estimate of $d = 0.7$. Based on this estimate, 88 participants would be required in each drink condition in a between-subjects design to achieve 90% power at an alpha level of 5%. However, as our alcohol/placebo condition will be within-subjects, we consider this a conservative estimate for our study, as we are using a within-subject design that will be less subject to less individual variation. We will recruit 44 participants per trait group (total $n = 88$). This would achieve 90% to detect an effect size of $d_z = 0.5$ (alcohol vs. placebo) within each trait group. Interaction analyses will be exploratory.

Withdrawal of participants

Participants will be informed that they can withdraw from the study at any time. If participants withdraw from the study due to an adverse event or reaction, they will receive full reimbursement (£20 or equivalent course credits). For all other withdrawals (i.e., not related to an adverse event or reaction), participants will be reimbursed an amount commensurate with the time spent in the laboratory.

Randomisation

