Computerised Tasks: Total hits and thresholds will be assessed for outliers using boxplots. Participant data will be removed if scores are 1.5 times greater than the interquartile range. Data will also be assessed for Normality using skewness and kurtosis statistics. Where Mauchly's Test of Sphericity is $p < .05$, Greenhouse-Geisser corrected statistics will be reported.

For 6AFC analysis, total hits will be analysed using a 2 drink (alcohol, placebo) \times 2 aggression (high, low) mixed model ANOVA to test emotion processing accuracy following an acute dose of alcohol. Interactions will be explored in post-hoc analyses using t-tests. To investigate processing accuracy of angry and sad faces following an acute dose of alcohol, emotion specific false alarms and hit rates will also be analysed using 2 drink (alcohol, placebo) \times 2 aggression (high, low) mixed ANOVAs; two for anger and two for sadness. The 2AFC data will be analysed using the same statistical model as the 6AFC total hit rate data to investigate whether there is an increased bias towards anger (happy-angry 2AFC) and a reduced bias towards sadness (happy-sad 2AFC) following an acute dose of alcohol. In addition, 6AFC hit rates will also be

analysed using an exploratory 2 drink (alcohol, placebo) × 2 aggression (high, low) × 6 emotion (happy, sad, angry, disgust, surprise, fear) mixed model ANOVA.

Questionnaire data will be analysed using 2 drink (alcohol, placebo) × 2 aggression (high, low) × 2 time (pre-consumption, post-consumption) mixed model ANOVAs. Interactions will be explored in post-hoc analyses using t-tests. Correlations between post-consumption state anger (S-Ang scores) and false alarms/hit rates (6AFC task) will be analysed using simple linear regression models.

Ethical Considerations and Informed Consent

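### The 50% male quota covers the whole sample, not each trait group, and no ANOVA includes sex, so the high-versus-low trait terms can be confounded with sex (minor; cheap to fix)

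*Protocol*

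**What the plan says.** Under Participants and Recruitment the sex target is attached to the total: "Male and female social alcohol drinkers (n = 88; 50% male) will be recruited". Under Sample size determination the split by trait is given without a sex split: "We will recruit 44 participants per trait group".

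Group membership comes from a screening score with one pair of cut-offs for both sexes: "Be high or low in trait aggression, defined by a score above 41 and below 32 on the Anger Expression Index subscale". The only randomised element (Randomisation) is the order of the two sessions.

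The Study Design section names "one between-subjects factor of trait" anger and no other. In the Statistical Plan, total hits go into a drink by "aggression (high, low) mixed model ANOVA to test emotion processing accuracy following an acute dose of alcohol". The other task outcomes follow the same form: "The 2AFC data will be analysed using the same statistical model as the 6AFC total hit rate data". Emotion or time is added in some models. Sex is not a factor, covariate or stratifier in any of them.

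The protocol does separate the sexes for eligibility: weekly drinking limits are 5–35 units for women and 10–50 for men, and the weight exclusion is "Weight less than 50 kg if female or 60 kg if male".

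Sample size determination also labels the interaction analyses exploratory.

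**The concern.** A quota on the total does not protect a comparison between two selected halves of that total. With 44 men and two groups of 44, the quota as written is met by 22 men in each group, by 33 and 11, or even by 44 and 0. Randomisation cannot correct this, because nobody is randomised to a trait group.

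Two results are exposed. The aggression main effect is biased if men and women differ in task performance. The drink × aggression interaction is biased if men and women differ in their response to alcohol. The sex-specific drinking limits add a further route: a sex imbalance between trait groups can bring an imbalance in habitual drinking with it.

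What is at stake is the interpretation of any high-versus-low difference, which the title and background make a natural thing to report. A difference attributed to trait aggression could partly be a sex difference.

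**Working it through.** **Inputs from the protocol.** Total 88, half of them men, so 44 men (Participants and Recruitment). 44 per trait group, alpha 5%, 90% power at dz = 0.5 within each group (Sample size determination). Alpha is taken as two-sided.

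**Assumed input.** The drink-by-sex difference δ, in SD units of the person-level alcohol-minus-placebo difference. The protocol gives no value, so 0.3, 0.5 and 0.8 are shown.

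**1. The plan's own figure.** Paired t-test, n = 44, dz = 0.5: noncentrality 0.5 × √44 = 3.317, power 0.900. The stated 90% reproduces. It concerns alcohol versus placebo within a trait group.

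**2. What the quota allows.** With m men in one group there are 44 − m in the other. The difference in male share is D = (2m − 44)/44, which can lie anywhere from 0 to 1 in size.

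**3. Which terms are affected.** Each person contributes an alcohol-minus-placebo difference. If that difference is δ larger in men, the group means differ by D × δ with no trait effect at all; this is the bias in the drink × aggression contrast. The aggression main effect has the same form, with δ replaced by the sex difference in the average over the two sessions. The alcohol-versus-placebo contrasts, overall or within one trait group, compare each person with themselves, so sex cannot confound them.

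**4. Chance imbalance.** If sex and trait are unrelated, m is hypergeometric (88 people, 44 men, 44 drawn). Two-sided probabilities:
- 26/18 or worse: 13.5%
- 29/15 or worse: 0.5%
- 31/13 or worse (about 70%/30%, since 0.70 × 44 = 30.8): 0.02%

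**5. False-positive rate of the interaction.** Noncentrality = D × δ × √(44/2) = D × δ × 4.690; two-sided t-test on 86 df.

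| Men | D | δ | Bias (SD) | Noncentrality | False-positive rate |
|---|---|---|---|---|---|
| 26/18 | 0.182 | 0.3 | 0.05 | 0.256 | 5.7% |
| 26/18 | 0.182 | 0.5 | 0.09 | 0.426 | 7.1% |
| 26/18 | 0.182 | 0.8 | 0.15 | 0.682 | 10.4% |
| 70%/30% | 0.40 | 0.3 | 0.12 | 0.563 | 8.6% |
| 70%/30% | 0.40 | 0.5 | 0.20 | 0.938 | 15.3% |
| 70%/30% | 0.40 | 0.8 | 0.32 | 1.501 | 31.7% |

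If the unmodelled sex difference is also counted in the error SD, as √(1 + δ²p(1 − p)) with p the male share, the 26/18 rates become 5.7%, 6.9% and 9.6%, and the 70%/30% rates about 9%, 15% and 29%. The picture is the same.

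**6. Average over chance splits.** Simulating whole trials with m drawn at random as in step 4 (100,000 per δ) gives rejection rates of 5.1%, 4.9% and 4.9%. With no link between sex and trait, there is no inflation over repeated trials; the rates in step 5 apply to a given realised split.

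**7. After the fix.** With 22 men and 22 women in each group, D = 0, so the bias is 0 and the false-positive rate does not exceed 5%. Each group still has 44 people, so the power in step 1 is still 90%.

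**The case against.** The best reply is that nothing the study is built to test is touched. H1–H5 are all alcohol against placebo, the sample size is set for those contrasts, and the interaction is labelled exploratory. No hypothesis concerns the aggression main effect. All of this stands, and it limits the point to secondary interpretation. It does not remove the point: an exploratory label does not correct a bias, and the aggression main effect does not carry that label.

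Second, serious inflation needs two things together: a marked imbalance and a sex difference in the response to alcohol. The protocol documents neither. A δ of 0.5 is as large as the whole alcohol effect the trial is powered for within a group, and the Background calls recent effect sizes small. Chance alone rarely gives more than a modest imbalance (step 4) and no inflation on average (step 6). This also stands. A reader might infer that the interaction will have a false-positive rate of 15% or more; the documents do not support that, because a 70%/30% split needs a link between sex and trait score or recruitment for which they give no figure.

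Third, the sex-specific eligibility limits do not show that sex affects face processing, and the all-male face stimuli are the same for both trait groups and create no imbalance. Both are fair.

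Fourth, 50% male may have been meant for each group, and covariate adjustment may be left to a statistical analysis plan that is not at hand. The first is possible, but the text ties the figure to n = 88. On the second, the missing sex term should carry little weight by itself. The quota, however, is a recruitment rule that belongs in the protocol, and later adjustment cannot restore a nearly empty sex-by-trait cell.

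**Conclusion.** The point holds as a minor one. A trial that followed the protocol exactly could end with trait groups that differ in sex composition, and the planned models would not separate the two. The exposure is confined to the aggression main effect and the exploratory drink × aggression interaction.

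At an imbalance that chance can plausibly produce (26/18), the interaction's false-positive rate moves from 5% to somewhere between 6% and 10%, depending on an assumed drink-by-sex difference of 0.3 to 0.8 SD. Anything much larger rests on a further assumption, an association of sex with trait score or with who is recruited, that the protocol leaves open.

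It would be wrong to conclude that the alcohol effects are confounded with sex, or that imbalance will occur. The text shows only that nothing prevents it.

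**What to change.** State the quota within trait group: 22 men and 22 women in the high group, and the same in the low group. This alone removes the bias from sex.

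As a second safeguard, include sex as a between-subjects factor, with its interaction with drink, when the aggression and drink × aggression terms are reported. This is useful mainly because withdrawals and the boxplot outlier rule can disturb the balance after recruitment.

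The total stays at 88 and the within-group power at 90%. Trait score is known from the online questionnaire before anyone is invited, so the quota can be applied at that step. The cost is that the scarcest sex-by-trait cell may fill more slowly. Balancing sex removes this one confounder only; trait groups may still differ in other ways, and the report should say so.

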Session order (i.e., alcohol vs. placebo) will be counterbalanced with equal numbers of participants in each order group. Participant numbers will be allocated session orders in advance of the study using random number generator software (www.randomizer.org).

Measures and Materials

Computerised Tasks: The images used in both tasks are composite (i.e., prototypical) images created from photographs of 12 young male adults photographed under controlled conditions. Each trial in both tasks begins with a centrally-displayed fixation cross. A 350×457 pixel face stimulus is then presented for 150 ms, followed by a noise mask for 250 ms in order to prevent after-image effects. Tasks are run using E-Prime 2.0 Pro software, on a standard computer with a QWERTY keyboard.

In the six-alternative forced choice task (6AFC), six 15-image morph sequences have been created, one for each emotion (happy, sad, angry, disgust, surprise and fear). These run along a linear continuum from a neutral (i.e., emotionally ambiguous) prototype to the full emotional intensity. On each trial, a single image from the 90

available is presented for 150ms (backward masked), and participants are required to identify the emotion represented in the face as quickly and as accurately as possible, by using the mouse to click on the most appropriate descriptor from an array of descriptors displayed on-screen (happy, sad, angry, disgust, surprise and fear). The descriptor array appears on-screen for 10,000 ms, or until the participant responds. Each image is presented twice, giving 180 trials in total.

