In addition, a happy-angry and a happy-sad two-alternative forced choice task (2AFC) will also be run. For each of these tasks, a 15-image morph sequence has been created, which runs from one full emotional exemplar to another (i.e., unambiguously happy to unambiguously angry / unambiguously happy to unambiguously sad). The full exemplar images are used as endpoints to create a linear morph sequence of emotionally ambiguous images that change incrementally from happy to angry in one task version and happy to sad in the other. On each trial of the happy-angry 2AFC task, a frame from this morph continuum is presented for 150 ms (backward masked), and participants are required to identify whether the emotion in the face is happiness or anger, by pressing designated keys on the keyboard. On each trial of the happy-sad 2AFC task, a frame from this morph continuum is presented for 150 ms (backward masked), and participants are required to identify whether the emotion in the face is happiness or sadness. Each image is presented three times, giving 45 trials in total for each 2AFC task.

Questionnaires: Trait aggression will be measured using the anger expression index subscale (AXi) of the State-Trait Anger Expression Inventory (STAXI-2) (Spielberger, 1999). This is a widely-used measure of aggression that has been validated on a variety of normal and clinical samples (Forgays, Forgays, & Spielberger, 1997). Normative data for the STAXI-2 scale are based on samples of normal adults (n=1,644) ranging from 16-63 years old; these data shows a mean score of 32.9 (SD = 13.4) for the AXi subscale. High and low trait groups will be defined by a score above the 60th percentile and below the 40th percentile on this subscale, respectively.

Other questionnaire measures will include the State Anger Subscale (S-Ang) of the STAXI-2 (Spielberger, 1999), Positive and Negative Affect Schedule (PANAS) (Watson, Clark, & Tellegen, 1988), Biphasic Alcohol Effects Scale (BAES) (Martin, Earleywine, Musty, Perrine, & Swift, 1993) and Alcohol Use Disorders Identification Test (AUDIT) (Saunders, Aasland, Babor, Delafuente, & Grant, 1993).

Procedure

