Prior to testing, participants will complete the STAXI-2 online. Only individuals that meet the high/low trait anger inclusion criteria will be invited to participate. On arrival at the first session, participants will be given the opportunity to read the information sheet again and ask questions, before providing written informed consent. The researcher will conduct a short screening procedure to verify eligibility, which includes taking measures of weight and breath alcohol concentration (BrAC) (only participants with a BrAC of zero will be enrolled). Study documentation from failed screenings will be destroyed using the School's confidential waste facility. If eligible, participants will complete questionnaire measures (AUDIT, PANAS, BAES, S-Ang).

Participants will attend two sessions (order counterbalanced): at one session they will consume an alcoholic drink and at the other they will consume a matched placebo drink (see Drug Administration section for more details). Testing sessions will be held at least one week apart. Participants will be given 10 minutes to consume all of their drink and a further 10 minutes to sit quietly to allow for absorption. After drink consumption, participants will complete the 6AFC and 2AFC tasks. They will then complete questionnaire measures (PANAS, BAES, S-Ang), and a BrAC reading. Before leaving the session, participants will be required to read and sign a safety card, be offered the opportunity to stay behind until they feel any effects of alcohol have worn off and be offered a taxi home. At the end of session two, participants will be debriefed and reimbursed.

Table 1: Testing procedure timeline

Time (min)	Activity/Task
0	Informed consent and screening (session one only)
10	Questionnaire measures (AUDIT, PANAS, BAES, S-Ang)
20	Drink administration
30	Alcohol absorption period
40	Computerised tasks
65	Questionnaire measures (PANAS, BAES, S-Ang), BrAC reading
75	Debrief and reimbursement (session two only).

Drug Administration

The alcoholic drink will be 0.4 g/kg alcohol (vodka) with one part vodka and three parts tonic water. The placebo drink will comprise the same volume of tonic. Drinks will be flavoured with lime cordial and chilled prior to serving. The rim of the glass will be sprayed with a vodka mist. Drinks will be served double blind and will be made at the start of each session by a research collaborator.

Statistical Plan

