Ethics approval has been obtained from the Faculty of Science Research Ethics Committee at the University of Bristol (approval code: 26011747361). The study will be conducted according to the revised Declaration of Helsinki (2013) and the 1996 ICH Guidelines for Good Clinical Practice E6(R1). The investigator will explain the nature, purpose and risks of the study to the participant. The participant will receive the information sheet in advance of the study session. There will be no time restriction on how long participants take to respond, with the exception that participants who respond after all study places have been filled will not be offered a place on the study. Therefore, participants will be given sufficient time to read the information, consider any implications, and raise any questions with the investigators prior to making a decision to participate. On arrival at the study session participants will be given the opportunity to read the information sheet again and ask the investigator questions. Written consent will then be obtained. Participants will be informed that they are free to withdraw at any time.

Safety

Participants will be administered alcohol during one of the sessions. The dose will be 0.4 g/kg of body weight up to 90 kg. Participants weighing more than 90 kg will receive a dose based on 90 kg. This dosing will administer drinks ranging between around 2.5 to 4.5 units of alcohol (for weight ranges between 50-90 kg). We expect that at this dose, participants will feel some effects of alcohol but we do not expect high levels of intoxication (all participants will be weekly alcohol consumers). However, to ensure the safety of our participants, they will know in advance of the study that they may receive this dose of alcohol, and therefore will be able to make any necessary arrangements. They will be advised that should stay behind until they feel the effects of alcohol have worn off and they shouldn't drive, operate heavy machinery or do anything that would be considered unsafe after drinking alcohol for the rest of the day. Participants who have received alcohol will be asked to read and sign a post-study safety form to confirm that they understand these risks. We have standard operating procedures in place for adverse effects of alcohol (i.e., nausea, intoxication) and have facilities for people to stay behind until they feel ready to leave. Participants will be offered a local taxi at the end of the session.

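### The exploratory drink × aggression interaction has no planned check for a difference in habitual drinking between the selected trait groups, although AUDIT is collected

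*Protocol*

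**What the plan says.** **Eligibility (Protocol, Inclusion criteria).** Habitual intake is bounded separately by sex: "Drinks between 5 and 35 alcoholic units* per week if female or between 10 and 50 alcoholic units* per week if male". Trait group rests on a questionnaire score alone: "Be high or low in trait aggression, defined by a score above 41 and below 32 on the Anger Expression Index subscale". No drinking criterion enters the group definition.

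**Balance.** Participants and Recruitment fixes the sex ratio for the whole sample: "Male and female social alcohol drinkers (n = 88; 50% male) will be recruited". It does not fix it within each trait group. Under Randomisation, the only thing allocated is session order: "Session order (i.e., alcohol vs. placebo) will be counterbalanced with equal numbers of participants in each order group".

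**Measurement.** Measures and Materials lists the "Alcohol Use Disorders Identification Test (AUDIT") among the questionnaires, and Procedure places it before the drink: "If eligible, participants will complete questionnaire measures (AUDIT, PANAS, BAES, S-Ang"). It is not among the post-drink questionnaires.

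**Models (Statistical Plan).** Total hits and the 2AFC thresholds are analysed by a drink × aggression mixed ANOVA. The emotion-specific hit rates and false alarms use the same model, "two for anger and two for sadness". An exploratory model for hit rates adds emotion. The questionnaire models add time, and the regressions use state anger. Neither AUDIT nor weekly units is a covariate anywhere.

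**Status of the interaction.** Sample size determination labels interaction analyses exploratory, and H1 to H5 are all alcohol-versus-placebo contrasts.

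**The concern.** Each participant serves as their own control for drink, so a stable characteristic such as habitual intake cannot bias the average alcohol-minus-placebo difference. That protection does not extend to comparing this difference between two selected groups. If high-trait and low-trait participants differ in habitual drinking, and drinking modifies the response to the dose, the drink × aggression term contains that modification as well as any effect of trait.

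This matters because the high-versus-low contrast is why the sample is selected at all. The Background speculates that alcohol may strengthen face-processing effects in people high in trait aggression, which is a statement about the interaction. The Statistical Plan puts the term in every task ANOVA and follows interactions with post-hoc t-tests. A reader will therefore want to know whether a group difference, or its absence, could be explained by drinking. The planned analysis offers no way to look, although a relevant measure is already collected.

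**Working it through.** **1. The protocol's own figure.** The stated 90% power for d_z = 0.5 with 44 per trait group is for the paired contrast within one group. The noncentrality is 0.5 × √44 = 3.317 on 43 degrees of freedom, and two-sided 5% power is 0.900. The figure reproduces. It concerns the within-person contrast, which this point leaves intact. (The protocol does not state sidedness; two-sided is assumed throughout.)

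**2. Room for a drinking difference.** From the eligibility limits: women 35/5 = 7-fold, men 50/10 = 5-fold. Across the whole sample the ratio is 50/5 = 10, but that joins the female minimum to the male maximum. The within-sex ranges are the fairer description. Sex balance is not stated by trait group, so the limits leave room for a difference both within and across sexes.

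**3. What an imbalance would do.** In a 2 × 2 mixed design the interaction test is a two-sample t-test on the alcohol-minus-placebo differences, here 44 against 44 (86 degrees of freedom, critical value 1.988). Let
- g = difference in habitual drinking between trait groups, in within-group SDs
- r = within-group correlation of drinking with the alcohol-minus-placebo difference

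With a true trait effect of zero, the spurious group difference is d = g × r in SDs of the difference score. The noncentrality is d × √(44/2) = 4.690 × d. Neither g nor r is in the protocol; both are assumptions.

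| g | r | d = g × r | noncentrality | P(reject), unadjusted |
|---|---|---|---|---|
| 0 | any | 0 | 0 | 5.0% |
| 0.25 | 0.3 | 0.075 | 0.352 | 6.4% |
| 0.5 | 0.3 | 0.15 | 0.704 | 10.7% |
| 0.8 | 0.4 | 0.32 | 1.501 | 31.7% |

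**4. What adjustment does.** In simulation (10,000 runs per row), regressing the difference score on trait group and drinking gave false-positive rates of 5.2%, 5.0%, 5.0% and 5.4% for the four rows, with r = 0.3 used in the first. This is the favourable case, in which the covariate is exactly the variable that modifies response. AUDIT would remove less to the extent that it is an imperfect measure of that variable.

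**5. Cost in precision.** The variance of the adjusted trait coefficient is multiplied by 1 + g²/4, before any gain from explained variance. At g = 0.8 that is 1.16, so the standard error grows by √1.16 = 1.077, about 8%, if drinking explains nothing. The factor (1 − r²) offsets this: at r = 0.4, √(1.16 × 0.84) = 0.987.

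**The case against.** The strongest reply is that no stated hypothesis is touched. H1 to H5 are within-person contrasts, the sample size is set for the alcohol effect overall and within each trait group, and the interaction is declared exploratory. This stands, and it limits the weight of the point. It does not remove it, because the exploratory term is the one that speaks to the study's rationale.

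Second, nothing in the protocol shows that the groups differ in drinking or that AUDIT predicts the response to alcohol. This also stands. A reader might infer that the interaction test will run at 7 to 32% instead of 5%. That range comes from choosing g between 0.5 and 0.8 and r between 0.2 and 0.4, which leaves out little or no gap; there the rate is 5 to 6%.

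Third, a reader might take the Safety remark, "we do not expect high levels of intoxication (all participants will be weekly alcohol consumers"), as the protocol conceding graded tolerance. It is a safety reassurance about a floor that all participants share and says nothing about differences within the eligible range.

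Fourth, the direction matters. If high-trait participants drink more and heavier drinkers react less, both of which are assumptions, spurious rejections mostly show a smaller alcohol effect in aggressive drinkers. Those in the direction the Background speculates about fall from 2.5% to 0.8% at d = 0.10 and 0.03% at d = 0.32. On those assumptions the risk is a masked or reversed interaction rather than false support for the rationale.

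Finally, a statistical analysis plan, not shown here, might add covariates. But the protocol itself sets out the ANOVAs without one, and unbalanced recruitment cannot be undone later. The reference to questionnaire data does not bring AUDIT into use either: that model needs a post-drink value, which AUDIT lacks, and it would treat AUDIT as an outcome.

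**Conclusion.** The point holds in a limited form. Trait groups are selected, drinking is not balanced between them, and the collected AUDIT score is in no task model. The drink × aggression interaction is therefore open to confounding by habitual drinking, with no planned check. The conclusions on H1 to H5 are not at risk.

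The size cannot be fixed from the protocol. The illustration runs from no inflation with no gap to about 32% for a gap of 0.8 SD with a correlation of 0.4, and it assumes a linear relation and 44 analysed participants per group. It shows what could happen, not what will. This is a worthwhile, low-cost improvement to an exploratory analysis and does not correct an error in a confirmatory one.

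**What to change.** 1. Tabulate AUDIT and the weekly units reported at screening by trait group, and by sex within trait group.
2. For each 6AFC and 2AFC outcome, add a sensitivity analysis that regresses the alcohol-minus-placebo difference on trait group and mean-centred AUDIT (or weekly units). This is equivalent to adding AUDIT and AUDIT × drink to the mixed model.
3. Report the drink × aggression estimate and its interval with and without adjustment, and say how far the estimate moves. Do not make attribution depend on whether significance survives: adjustment can widen the interval without any confounding, so a real difference could fail such a rule.
4. Describe any difference between trait groups as an association. One covariate does not turn a selected factor into a causal one.

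The cost is a few sentences in the Statistical Plan, one table, one degree of freedom per model, and a wider interval if drinking and trait are correlated. AUDIT is already collected. Weekly units are needed for eligibility, but they should be copied into the study dataset if they sit only in the screening records, because the protocol plans to destroy those.
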